### **5.5.2 Non-Investigational Medicinal Products**

Starting from the screening visit, participants will be instructed to use a topical emollient (moisturizer) daily.

### **5.5.3 Permitted Concomitant Therapy**

Subjects may continue prescribed topical therapies throughout the trial which will be documented by site staff. Appropriate interventions (e.g., prescribed medications) may be performed as the investigator deems necessary to treat concomitant illnesses and/or safeguard the subjects' wellbeing. No investigational product or device may be used during the study.

## **5.6 Study Procedures**

### **5.6.1 Informed Consent**

This Study will be conducted in compliance with CFR Title 21, Part 50 (Informed Consent of Human Subjects). Informed consent will be obtained from each subject in writing before participation in the Study. A signed copy of the Informed Consent Form will be provided to each subject. A provision to obtain a signed authorization to provide protected health information to the study sponsor, internal quality assurance agencies, health insurance agencies, and other parties as specified in the Federal Health Insurance Portability and Accountability Act (HIPAA) privacy regulation will be included in the Informed Consent Document. HIPAA authorization is voluntary. However, since the use and release of health information is critical to the conduct of the study, subjects who do not provide authorization to use and disclose their health information will not be enrolled into the study. Subjects who withdraw their authorization to use and release health information during study participation will be formally discontinued from the study. The investigator may use and release at any time all the information collected prior to a subject's withdrawal of the authorization to all authorized parties to satisfy scientific, regulatory, and financial concerns.

### **5.6.2 Inclusion and Exclusion Criteria**

Subjects' eligibility to participate in the study will be determined according to the Inclusion and Exclusion Criteria during the screening period (0 – 30 days prior to the first dose of the study drug). Subjects who ultimately do not satisfy the eligibility criteria except changing treatments and undergoing a washout period, will not be enrolled into the study. Investigator will confirm any adverse events experienced on dupilumab treatment will be fully resolved prior to initiating tralokinumab. Subjects who need to meet eligibility requirements will be asked to make the necessary changes. Subjects who agree and comply will be re-evaluated prior to initiation dosing.

### **5.6.3 Demographics and Medical History**

The following information will be obtained for each subject during screening: date of birth, sex, race/ ethnic origin, medical and surgical history, year of diagnosis of atopic dermatitis, current atopic dermatitis treatments, and other previous atopic dermatitis treatments within the last 6 months. All current therapies for other medical conditions will be documented. Medical history will be reviewed and updated at the Baseline Visit to ensure that the patient remains eligible to participate in the study.

### **5.6.4 Pregnancy Test**

Urine Pregnancy testing will be conducted in all female subjects, except those without childbearing potential (e.g., one-year post-menopause, post-hysterectomy, post-bilateral oophorectomy, etc.) at Screening Visit & Week 0, prior to the first dose of tralokinumab. Subjects with a positive pregnancy test will not be eligible to participate or to continue to receive study treatment.

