### **5.6.5 Physical Examination**

A physical examination, including vital signs measurements (blood pressure, pulse and temperature), will be performed at each study visit. Any clinically significant abnormalities discovered during physical examinations after the Screening visit should be documented and evaluated as potential adverse events.

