### **5.6.11 Early Discontinuation Procedures**

Subjects will be prematurely discontinued from the study under the following conditions:

1. Subject requests to withdraw from the study.
2. Subject is noncompliant with protocol schedule, restrictions, and/or requirements.
3. Subject experiences an adverse event that makes it difficult or intolerable for the subject to continue treatment, or increases risk to the subject, or interferes with the investigator's ability to clinically evaluate the progress of the subject's treatment.
4. Subject begins an unapproved concomitant therapy for atopic dermatitis or another medical condition that may increase risk to the subject if continuing study treatment.
5. Subject cannot be reached / lost to follow-up.
6. The study investigator suspends or terminates the study.
7. Other unanticipated reason.

Any subject who prematurely discontinues the study should complete the week 24 (End of Study) assessments. Any subject who withdraws consent to participate in the study will be removed from further treatment and/or study observation immediately upon the date of request.

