## 6 Adverse Events

### 6.1 Adverse Events (AEs)

An adverse event (AE) is any untoward occurrence in a subject, whether or not related to the product. An AE does not necessarily have to have a causal relationship with the study treatment. AEs include events not present at baseline and events that worsened if present at baseline. Hospitalizations for pre-treatment conditions (e.g., elective cosmetic procedures) or surgeries that were planned prior to entry into the study are not considered adverse events. Adverse events, regardless of causality, will be captured from the signing of the Informed Consent Form and for the duration of the subject's participation. Events will be captured as observations from investigator or events reported by subjects from the signing of the informed consent form.

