### **6.3 Pregnancy Reporting**

The investigator will follow the pregnancy and outcome. Any information gained will be documented in the subject source documents and reported as per local guidelines. Female subjects who become pregnant will be discontinued from study treatment.

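### No pregnancy test is scheduled after the first dose, so during treatment the pregnancy stopping rules depend on indirect detection; adding urine tests at existing dispensing visits is a cheap safety improvement

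*Combined protocol and SAP*

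**What the plan says.** Section 5.6.4 (Pregnancy Test) sets the timing of urine testing for women who could conceive: "at Screening Visit & Week 0, prior to the first dose of tralokinumab". The Urine Pregnancy Test row of the Schedule of Assessments agrees. It is marked at Screening and Baseline and blank at Weeks 4 to 24.

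Two rules apply to pregnancy during treatment. Section 5.6.4 states: "Subjects with a positive pregnancy test will not be eligible to participate or to continue to receive study treatment". Section 6.3 (Pregnancy Reporting) states: "Female subjects who become pregnant will be discontinued from study treatment". It adds: "The investigator will follow the pregnancy and outcome".

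Other provisions bear on the point:
- **Prevention.** Section 5.2.1 requires contraception where conception is possible, and 5.2.2 excludes women planning a pregnancy. Section 5.6.11 lists as a reason for discontinuation: "Subject is noncompliant with protocol schedule, restrictions, and/or requirements".
- **Indirect detection.** Section 6.1 says of adverse events: "Events will be captured as observations from investigator or events reported by subjects". Section 5.6.5 says: "Any clinically significant abnormalities discovered during physical examinations after the Screening visit should be documented and evaluated as potential adverse events". Adverse events and concomitant medications are reviewed at every visit.
- **Supply.** IP Dispensing and Accountability is marked at Baseline and at every later visit.

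**The concern.** The protocol has already decided that pregnancy must stop dosing, and 5.6.4 applies that to subjects on treatment as well as at entry. Both scheduled tests come before the first dose, so neither can trigger that part of the rule. The rule therefore depends on someone first suspecting a pregnancy.

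Subject safety is what is at stake. A urine test at a visit where drug is handed out could show a pregnancy before the subject or the investigator notices it, and dosing could stop sooner.

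**Working it through.** The plan has no figure of its own to reproduce on this point. The check is a count of visits and doses, with the relevant provisions set side by side.

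**Inputs**
- Scheduled tests: Screening and Week 0 (5.6.4 and Schedule of Assessments).
- Post-baseline visits: Weeks 4, 8, 12, 16, 20 and 24, which is 6 visits, all marked for IP Dispensing and Accountability (Schedule of Assessments).
- Dosing: loading dose at Week 0, then every two weeks for 24 weeks (5.1). Whether a dose is given at Week 24 itself is not stated, so both cases are shown.
- Planned enrolment: 20 subjects (5.1, 5.4). The number of females of childbearing potential is not given.

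**Current plan**
- Scheduled tests: 2 before the first dose, 0 after it.
- Dosing occasions after the last scheduled test: Weeks 0, 2, ..., 22, so 22/2 + 1 = 12, or 13 with a Week 24 dose.

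**With tests before dispensing at Weeks 4, 8, 12, 16 and 20** (nominal schedule)

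| From test at | Dosing occasions before the next test | Count |
|---|---|---|
| Week 0 | 0, 2 | 2 |
| Week 4 | 4, 6 | 2 |
| Week 8 | 8, 10 | 2 |
| Week 12 | 12, 14 | 2 |
| Week 16 | 16, 18 | 2 |
| Week 20 (last) | 20, 22 | 2 (3 if a Week 24 dose is given and no Week 24 test is done) |

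A Week 24 test would precede 0 doses, or 1 if a Week 24 dose is given.

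**Number of tests.** 5 × n with n from 0 to 20 gives 0 to 100 dipsticks. With Week 24 added, 6 × n gives 0 to 120.

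**Could the existing routes serve as a scheduled trigger?**
- Adverse event capture (6.1) depends on an observation or a report, and that section does not name pregnancy.
- Examination (5.6.5) is called for at each visit, although the schedule row is blank at Week 4. It finds only what is clinically apparent.
- Concomitant-medication review might reveal a stopped hormonal contraceptive or a new prenatal product.
- An unscheduled test is possible, but nothing in the protocol requires one, for example after a missed period.
- Contraception, the exclusion of planned pregnancy and discontinuation for noncompliance lower the chance of pregnancy but do not detect one.

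Each detection route works only once someone has noticed something.

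**The case against.** The strongest reply is that this is a preference about testing frequency, not a defect. Section 6.3 stops treatment for pregnancy however it is discovered, and 5.6.4 does not limit itself to scheduled tests. A stopping rule is coherent without a screening test behind it. The documents describe no fetal risk and cite no requirement for on-treatment testing, and the existing preventive controls are substantial. All of this stands, and it is why the point is put as an improvement.

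Three practical objections also stand and shape the fix:
- The protocol does not say how many syringes are dispensed at each visit. Self-injection is allowed (5.5.1.2) and missed doses may be skipped (5.5.1.3), so drug may remain at home. Withholding the next supply would not by itself stop dosing.
- Repeating a positive test adds a confirmation step that 5.6.4 does not contain, so it needs its own wording.
- The 2-dose figure is the spacing between tests. It does not limit exposure after conception, because a very early pregnancy can test negative.

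A reader might go further and infer that the protocol contradicts itself, that its stopping rules cannot operate, or that no examination takes place at Week 4. The documents support none of these. The rules can operate through the indirect routes. The Week 4 examination is an inconsistency between 5.6.5 and the schedule, and it does not show that the examination is absent.

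The reply does not answer the narrower point. The protocol already wants dosing stopped on pregnancy, already uses a urine test, and already has visits at which the test could be done.

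**Conclusion.** The point holds as a low-cost patient-safety improvement that should be made. It is not an error in the plan. Scheduled tests after the first dose would rise from 0 to 5. Consecutive tests would be at most 2 dosing occasions apart, where now all 12 nominal occasions (13 with a Week 24 dose) follow the last scheduled test.

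This rests on the nominal visit and dosing schedule and on text and table agreeing about test timing, which they do. The number of subjects affected, the pregnancy rate, the delay in detection and the exposure avoided cannot be estimated from the documents, and none is claimed. The consent form was not available, and nothing is inferred from that. The primary endpoint, sample size and analysis are unaffected.

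**What to change.** 1. Extend the Urine Pregnancy Test row of the Schedule of Assessments, and the timing in 5.6.4, to Weeks 4, 8, 12, 16 and 20 for females of childbearing potential, with the test done before IP is dispensed.
2. Add to 5.6.4: if an on-treatment test is positive, IP is not dispensed, the subject is told to stop dosing (including any syringes held at home), and the test is repeated promptly. A confirmed positive leads to discontinuation and follow-up under 6.3.
3. Optionally add Week 24. Its purpose would be follow-up under 6.3, not the prevention of doses. It would also cover early discontinuers, since 5.6.11 says: "Any subject who prematurely discontinues the study should complete the week 24 (End of Study) assessments".

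**Cost.** 0 to 100 dipsticks (0 to 120 with Week 24) at visits that already take place, one schedule row, and revised timing plus a short confirmation rule in 5.6.4. No new visit, staff or invasive procedure is needed. An occasional false positive may delay a dose. If the repeat result comes too late for the 7-day missed-dose window in 5.5.1.3, that dose is skipped.

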### **5.6.5 Physical Examination**

A physical examination, including vital signs measurements (blood pressure, pulse and temperature), will be performed at each study visit. Any clinically significant abnormalities discovered during physical examinations after the Screening visit should be documented and evaluated as potential adverse events.

### **5.6.6 Investigator's Global Assessment (IGA)**

IGA will be determined for all subjects throughout the study. The Investigator's Global Assessment of atopic dermatitis is scored on a 5-point scale (0-4), evaluating global erythema, induration and scaling. [See Appendix A](#)

### **5.6.8 Body Surface Area (BSA)**

BSA will be determined for all subjects throughout the study. The subjects palm will be selected for the measuring unit of body surface area. The physician will equate the number of palms affected by atopic dermatitis to derive the BSA total.

### **5.6.9 Photography**

A target region/lesion representative of subject's disease will be selected by the investigator at baseline and photographed at weeks 0, 4, 8, 12, 16, 20 & 24.

### **5.6.10 Patient Reported Outcomes**

#### **5.6.10.1 Dermatology Life Quality Index (DLQI)**

Subjects will complete the Dermatology Life Quality Index (DLQI) at weeks 0, 4, 8, 12, 16, 20 and 24. [See Appendix B](#)

#### **5.6.10.2 Pruritis Numerical Rating Scale (Pruritis NRS)**

Subjects will complete a pruritis numerical rating scale to assess patient itch intensity over the previous 24 hours. Patients will be asked On a scale of 0 to 10, how would you rate your itch overall (on average) during the previous 24 hours? Where 0=no itch and 10=worst imaginable itch. [See Appendix C](#)

### **5.6.11 Early Discontinuation Procedures**

Subjects will be prematurely discontinued from the study under the following conditions:

1. Subject requests to withdraw from the study.
2. Subject is noncompliant with protocol schedule, restrictions, and/or requirements.
3. Subject experiences an adverse event that makes it difficult or intolerable for the subject to continue treatment, or increases risk to the subject, or interferes with the investigator's ability to clinically evaluate the progress of the subject's treatment.
4. Subject begins an unapproved concomitant therapy for atopic dermatitis or another medical condition that may increase risk to the subject if continuing study treatment.
5. Subject cannot be reached / lost to follow-up.
6. The study investigator suspends or terminates the study.
7. Other unanticipated reason.

Any subject who prematurely discontinues the study should complete the week 24 (End of Study) assessments. Any subject who withdraws consent to participate in the study will be removed from further treatment and/or study observation immediately upon the date of request.

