#### **5.5.1.3 Tralokinumab Dosage Adjustments**

If an adverse event that is thought to be related to tralokinumab and is not alleviated by symptomatic intervention, tralokinumab may be temporarily or permanently discontinued. If an adverse event causes the delay of administering tralokinumab, the dose may be

administered once the event has resolved or is stable in the opinion of the investigator. If an Q2W week dose is missed, the patient should administer the injection within 7 days from the missed dose and then resume the patient's original schedule. If the missed dose is not administered within 7 days, instruct the patient to wait until the next dose on the original schedule. Subjects who permanently discontinue tralokinumab under this protocol should receive standard care of atopic dermatitis treatment as prescribed by their physician.

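### Section 5.6.11 takes a subject with a treatment-limiting adverse event out of the study, not only off tralokinumab, and leaves one undated assessment to cover what follows

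*Combined protocol and SAP*

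**What the plan says.** Protocol 5.6.11 (Early Discontinuation Procedures) opens its list with "Subjects will be prematurely discontinued from the study under the following conditions". Item 3 begins "Subject experiences an adverse event that makes it difficult or intolerable for the subject to continue treatment, or increases risk to the subject". The rule is mandatory, and what the subject leaves is the study. The section then adds "Any subject who prematurely discontinues the study should complete the week 24 (End of Study) assessments", without saying whether this happens when the subject leaves or when week 24 arrives. Only withdrawal of consent is said to end observation at once.

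Protocol 5.5.1.3 (Tralokinumab Dosage Adjustments) deals with the drug separately. For a related AE that symptomatic treatment does not relieve, "tralokinumab may be temporarily or permanently discontinued". A delayed dose may be given once the event has settled, so a temporary hold presupposes that the subject stays in. For a permanent stop the only provision is "Subjects who permanently discontinue tralokinumab under this protocol should receive standard care of atopic dermatitis treatment as prescribed by their physician". Study visits are not mentioned.

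Protocol 6.1 collects AEs from consent "for the duration of the subject's participation", and adds "Events will be captured as observations from investigator or events reported by subjects". The Schedule of Assessments marks AEs at every visit and has no early-termination or safety follow-up column. For pregnancy, 6.3 stops treatment and says "The investigator will follow the pregnancy and outcome". Sections 6.1 to 6.2.1 have no matching sentence for an AE that ends treatment.

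**The concern.** Stopping a drug and leaving a study are separate decisions, and item 3 merges them for the subjects whose safety follow-up is most informative. Safety is a secondary objective in the Synopsis, and AEs and SAEs are listed among the endpoints. Section 5.2.1 admits people who stopped dupilumab for intolerance or AEs, so tolerability of the second drug is a central question. With about 20 subjects and no control arm, each treatment-limiting event is a large share of the safety evidence.

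At stake is what happens after the stop: whether the event resolved off drug, how long that took, what treatment it needed, and whether other events followed.

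**Working it through.** The plan gives no figure to reproduce, so this is a count from the Schedule of Assessments.

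**Inputs.** Post-baseline AE visits: weeks 4, 8, 12, 16, 20 and 24, six in all. Assessments after early discontinuation (5.6.11): one. End of planned follow-up: week 24.

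**Formulas.** Visits lost = AE visits left on the schedule − 1. If End of Study is done at exit, the longest shortening of AE capture = 24 − week of removal.

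| Removal | AE visits left | Under 5.6.11 | Visits lost | Longest shortening if done at exit |
|---|---|---|---|---|
| before week 4 | 6 | 1 | 5 | more than 20 weeks |
| just after week 4 | 5 | 1 | 4 | 24 − 4 = 20 weeks |
| just after week 8 | 4 | 1 | 3 | 24 − 8 = 16 weeks |
| just after week 12 | 3 | 1 | 2 | 24 − 12 = 12 weeks |
| just after week 16 | 2 | 1 | 1 | 24 − 16 = 8 weeks |
| just after week 20 | 1 | 1 | 0 | 24 − 20 = 4 weeks |

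The last column applies only if the assessment is done at exit. If it is done at calendar week 24, the same intervals carry one visit at their end in place of visits every 4 weeks, and subject-reported events can still be captured there, with longer recall.

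**How many subjects.** The documents give no rate of permanent stops for AEs. Taking 2%, 5% or 10% purely as assumptions, with independent subjects and n = 20:
- Expected number affected: 20 × 0.02 = 0.4; 20 × 0.05 = 1; 20 × 0.10 = 2.
- Chance that nobody is affected: 0.98^20 ≈ 67%; 0.95^20 ≈ 36%; 0.90^20 ≈ 12%.

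**IGA.** On either timing, a subject removed before week 16 has no scheduled week-16 IGA. I give no IGA visit counts, because the Schedule leaves week 4 blank for IGA while the secondary endpoints in 8.2 include week 4.

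**Net visits added by staying on schedule.** For a stop before week 16, keeping only weeks 16 and 24 adds 2 − 1 = 1. Keeping every remaining visit adds up to 5 − 1 = 4 after week 4, or 6 − 1 = 5 for a stop before week 4.

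**The case against.** The strongest reply is that this is a small, open-label, exploratory study, and exit with a closing assessment is a defensible design. Item 3 applies only once the investigator knows of the event, so that AE is already recorded. The closing assessment includes AEs, IGA, physical examination and vital signs. Observation is cut off at once only on withdrawal of consent. If the closing assessment falls at calendar week 24, participation, and with it AE capture, arguably runs until then. Visit counts are not information, and possibly no subject will be affected.

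Much of this stands, and it rules out several stronger readings that a reader might infer:

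- *The treatment-limiting AE goes unrecorded.* Section 6.1 captures it. Only its later course and later off-drug events are at risk.
- *12 to 20 weeks of capture are certainly lost.* That needs the exit reading, which the text neither states nor excludes.
- *Any AE-related interruption leads to removal.* Section 5.5.1.3 allows holds and resumed dosing, so the gap concerns permanent stops.
- *Item 3 shifts the primary proportion.* One missing week-16 IGA is worth 1/20 = 5 percentage points, but that comes from the absence of a counting rule in 8.2, a separate matter affecting any missing week-16 value. Under a non-responder rule the subject counts as 0/20 whether or not seen at week 16, so retention moves the primary estimate by 0.
- *Section 6.3 is a model for keeping visits.* It follows the pregnancy and its outcome but does not keep the subject on the schedule. It shows only that the protocol asks for outcome follow-up elsewhere.

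What the reply does not answer is that one assessment of unstated timing is a poor record of an event's course. Done at exit, it may come before resolution; done at week 24, it may rest on months of recall. Stopping the drug already protects the subject, and observation adds no exposure.

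**Conclusion.** The point holds as a weakness in safety follow-up after a permanent stop for an AE. Following the stated rule costs 5, 4, 3, 2, 1 or 0 scheduled AE visits per affected subject, for removal before week 4 or after week 4, 8, 12, 16 or 20. On the exit reading, capture also ends up to 20, 16 or 12 weeks early for removal just after week 4, 8 or 12.

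This rests on the Schedule as printed and on subjects who have not withdrawn consent. The trial-wide effect cannot be stated, because no stop rate is given. The change should be made because it is cheap and serves a stated objective. The primary endpoint does not depend on it.

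**What to change.** 1. In 5.6.11, make item 3 a reason to stop tralokinumab, not to leave the study. Leave holds and missed doses to 5.5.1.3.
2. Keep subjects who permanently stop the drug, and have not withdrawn consent, on visits already scheduled, at least weeks 16 and 24, for AE and IGA collection.
3. Follow the AE that led to the stop until it resolves or is stable, and record any standard care started. Word item 4 of 5.6.11 so that standard care begun after the stop does not itself cause removal.
4. If a subject declines further visits, do the End of Study assessments at exit, and say so in 5.6.11.

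The cost is a net 1 to 5 already planned visits per affected subject who stops before week 16, plus an IRB amendment and consent wording, since subjects would be asked to attend while under their own physician's care. Step 4 alone would settle the timing but would not restore follow-up of the event. The counting rule for a missing week-16 IGA should be dealt with separately.
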